5.9.3 Definition of Maximum Tolerated Dose

The MTD is defined as the dose at which ≤ 1 of 6 patients experiences a treatment-related toxicity that qualifies as a DLT, with the next higher dose having ≥ 2 of up to 6 patients experiencing a DLT.

The MTD will not be established until all patients enrolled in the cohort have completed Cycle 1, discontinued treatment or had a dose reduction. Previously established tolerability of a dose level will be reevaluated if toxicities that would have been DLTs in Cycle 1 are observed in later cycles.

5.9.4 Definition of Optimal Biological Dose (OBD)

For each treatment arm, the safety review committee might identify an OBD for a selected patient population before the MTD is reached. Such OBD would be derived from the evaluation of available safety, PK, PD, and preliminary efficacy information from the dose escalation portion of the study.

5.10 Concomitant Medications and Therapies

5.10.1 Permitted and Recommended Medications

Any changes in documented, permitted concomitant medications taken within 28 days of beginning treatment with ALRN-6924, or at the beginning of the clinical trial, or permitted concomitant medications added during the time the patient is participating in this study (through End-of-Treatment Visit or receipt of a subsequent therapy) must be recorded in the eCRF. All supportive medications and medications to treat toxicities as listed in Section 5.4 must be recorded in the eCRF.

Patients treated with ALRN-6924 have experienced nausea and vomiting. The administration of antiemetics, including 5HT3 antagonists, is recommended prior to and for 72 hours following

ALRN-6924 administration. For patients receiving palbociclib, additional antiemetic administration may be required.

Patients who experience neutropenia after Cycle 1 of DEP or at any time during EXP may receive myeloid growth factors at the discretion of the investigator.

5.10.2 Prohibited Medications and Medications Requiring Special Consideration

Other agents and treatments as outlined in Section 4, including concurrent anti-tumor therapy of any kind or any other investigational agent, are excluded. In the event that a patient is deriving clinical benefit from study treatment, but requires concurrent anticancer surgery or radiation therapy, that patient may continue on the study with permission of the Medical Monitor. The PI and medical monitor will determine the required duration of ALRN-6924 and/or palbociclib interruption, to allow for such treatments. Efficacy measures will be censored, as of the time of any such permitted concurrent therapy.

Although they are not prohibited, it is strongly recommended that alternative antihypertensive agents be used in place of ACE inhibitors and ARBs during treatment with ALRN-6924. It cannot be excluded that concomitant treatment with these agents and ALRN-6924 may increase the risk for developing angioedema. Note that this does not change the requirement to hold ARBs for 48 hours following the administration of ALRN-6924, due to a known pharmacokinetic interaction that decreases clearance of the ARB.

Any concomitant medications that are predominantly cleared by hepatobiliary transporters, OATP members OATP1B1 and OATP1B3, on the day of the ALRN-6924 infusion and within 48 hours after an ALRN-6924 infusion are prohibited ([Appendix B](#)), including the sartan class of angiotensin receptor blockers (ARBs).

For patients with MDM2 amplified or MDM2/CDK4 co-amplified solid tumors who are receiving ALRN-6924 in combination with palbociclib, strong CYP3A inhibitors and moderate to strong CYP3A inducers are prohibited. Patients should not consume grapefruit products while receiving palbociclib.

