7.6 Clinical Activity Analysis

To evaluate clinical activity, response rates and duration of response based on RECIST 1.1, IWG 2014, RANO, iRECIST, or other appropriate or exploratory criteria will be analyzed.

In DEP, the efficacy evaluable population will consist of patients who:

- Received at least one dose of ALRN-6924 at a dose level at least 0.8 mg/kg per infusion
- Have at least one post-baseline evaluation or had clinical progression and
- Are TP53 wild type or indeterminate (as assessed by the central lab, and if not assessed by central laboratory, as assessed by the local laboratory)

In the single agent EXP cohorts, the efficacy evaluable population will consist of patients who:

- Received at least one dose of ALRN-6924
- Have at least one post-baseline evaluation or had clinical progression and
- Are TP53 wild type (as assessed by the central lab)

In the EXP cohort of patients with MDM2 amplified or MDM2/CDK4 co-amplified solid tumors, the efficacy evaluable population will consist of patients who:

- Received at least one dose each of ALRN-6924 and palbociclib
- Have at least one post-baseline evaluation or had clinical progression and
- Are confirmed to have MDM2 amplification (with or without CDK4 co-amplification) with TP53 and Rb wild type (as assessed by the central lab)

A descriptive analysis of other evidence of anti-tumor activity or other clinical benefit will be provided based on clinical, radiographic or other appropriate assessment of efficacy or clinical anti-tumor activity.

Overall response rate, duration of response, and time to response will be assessed in DEP as well as in EXP.

Additional clinical activity analyses in the Phase 2a dose expansion will include OS and PFS and OS at 1 year. Time-to-event endpoints will be calculated from the time of first administration of ALRN-6924 (Day 1) until the stated event or end of study.

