4.2. CLINICAL ACTIVITY ENDPOINTS

- Overall response - objective evidence of complete response (CR) or partial response (PR). The evaluation of overall response will be based on response, as determined by the investigator, in accordance with RECIST version 1.1, for subjects with solid tumors, or IWG 2014 criteria, for subjects with lymphomas.

- Overall Response Rate (ORR) - proportion of subjects with overall response
- Time to Response (TTR) - time from the date of the first dose of ALRN-6924 to the date of the first documentation of overall response. The TTR will be calculated as follows (in months):

$$(\text{date of first response (CR/PR)} - \text{first dose date} + 1)/30$$

Subjects who do not respond will be censored at their last tumor assessment.

- Duration of Response (DOR) - time from the first documentation of overall response to the first documentation of objective or clinical disease progression or death due to any cause. This endpoint is only assessed among subjects who achieve overall response at some point during the study. The DOR will be calculated as follows (in months):

$$(\text{date of disease progression/death} - \text{date of first response (either CR or PR)} + 1)/30$$

Version V.1

Subjects who do not have disease progression (or death) will be censored at the last known time point that the subject was progression-free. Subjects with two or more consecutive missing response assessments prior to a visit with progression (or death) will be censored at the last date of tumor assessment when the subject was known to be progression free.

- Disease control - objective evidence of CR, PR, or stable disease (SD). The evaluation of disease control will be based on response, as determined by the investigator, in accordance with RECIST version 1.1, for subjects with solid tumors, and IWG 2014 criteria, for subjects with lymphomas.
 - Disease Control Rate (DCR) - proportion of subjects with objective evidence of disease control
 - Duration of Clinical Benefit (DCB) - time from the first documentation of disease control to the first documentation of objective or clinical disease progression or death due to any cause. This endpoint is only assessed among subjects who achieve disease control at some point during the study. The DCB will be calculated as follows (in months):

(date of disease progression/death - date of first response (either CR/PR/SD) + 1)/30

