Subjects who do not have disease progression (or death) will be censored at the last known time point that the subject was progression-free. Subjects with two or more consecutive missing response assessments prior to a visit with progression (or death) will be censored at the last date of tumor assessment when the subject was known to be progression free.

- Best Overall Response (BOR) - the highest level of objective response recorded (complete response, partial response, stable disease, or progressive disease) for each subject
- Progression-free Survival (PFS), defined as the time from the date of the first dose of ALRN-6924 to the date of first evidence of objective or clinical disease progression or the date of death, due to any cause, whichever occurs first. The PFS will be calculated as follows (in months):

(date of disease progression/death - first dose date + 1)/30

Subjects who do not have disease progression (or death) will be censored at the last known time point that the subject was progression-free. Subjects with two or more consecutive missing response assessments prior to a visit with progression (or death) will be censored at the last date of tumor assessment when the subject was known to be progression free.

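### The Phase 1 SAP has no rule for the protocol's censoring of efficacy at permitted concurrent surgery or radiation, and does not declare the omission

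*Protocol*

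**What the plan says.** Protocol 5.10.2 excludes concurrent anti-tumor therapy, with one exception. Where a patient is benefiting from study treatment but "requires concurrent anticancer surgery or radiation therapy, that patient may continue on the study with permission of the Medical Monitor". The rule for analysis follows: "Efficacy measures will be censored, as of the time of any such permitted concurrent therapy."

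The protocol's statistical section does not repeat it. Protocol 7.6 says: "Time-to-event endpoints will be calculated from the time of first administration of ALRN-6924 (Day 1) until the stated event or end of study."

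SAP 4.2 defines the Phase 1 clinical activity endpoints.
- PFS, DOR and DCB have two censoring rules. The first is: "Subjects who do not have disease progression (or death) will be censored at the last known time point that the subject was progression-free." The second begins: "Subjects with two or more consecutive missing response assessments prior to a visit with progression (or death) will be censored", and sets the date at the last assessment known to be free of progression.
- TTR has one rule: "Subjects who do not respond will be censored at their last tumor assessment."
- BOR is "the highest level of objective response recorded". ORR and DCR are proportions with no limit on which assessments count.

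SAP 9 adds Kaplan-Meier percentiles and Wilson intervals but no cut-off. SAP 11 says that the plan rests on Amendment 6 of 20 October 2017, and the only difference from the protocol that it names is the added DCB endpoint. SAP 3.1 limits the plan to Phase 1 and leaves Phase 2a to a separate plan.

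**The concern.** The two documents give different instructions for the same patients. A programmer working from the SAP would keep assessments and event times that protocol 5.10.2 removes, and nothing in the SAP would flag it.

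For response, the worry is attribution. If a target lesion is cut out or irradiated, the tumor sum can fall for reasons unrelated to ALRN-6924, and the SAP does not exclude the later scan. For the time-to-event endpoints, follow-up after the procedure mixes the effects of drug and local therapy.

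Phase 1 activity is a secondary objective and is reported descriptively, but single responses carry weight here. SAP 3.1 tabulates by dose cohort. Protocol 5.9.4 lets preliminary efficacy inform the optimal biological dose. Protocol 5.7.2 cites one complete remission when explaining the first PTCL expansion dose.

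**Working it through.** No figure in the plan bears on this point, so there is none to reproduce. The check is a comparison of texts, followed by illustrations on assumed data.

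**1. Rules side by side**

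| Endpoint | Protocol 5.10.2 | SAP 4.2 |
|---|---|---|
| PFS, DOR, DCB | censor at the procedure | censor only if there is no event, or after two or more missed assessments in a row |
| TTR | censor at the procedure | censor only if there is no response |
| BOR, ORR, DCR | censor at the procedure (meaning for a proportion not defined) | no cut-off |

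**2. Does Appendix K (RECIST 1.1) close the gap?** Its section 1.2 deals with lesions treated locally before study, not with a target lesion treated on study. Section 3.4 runs best response from start of treatment to progression, with no stop at local therapy. Section 3.1.2 records a lesion judged to have disappeared as 0 mm. The four-week confirmation in 4.1 does not help, because a resected lesion stays absent.

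Assumed example: two target lesions of 60 and 30 mm, unchanged on drug.
- Baseline sum: 60 + 30 = 90 mm. Change on drug: 0%, stable disease.
- 30 mm lesion resected and scored 0: sum 60 mm; change (60 − 90)/90 = −33.3%, past the 30% threshold for PR.

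With the 5.10.2 cut-off this patient stays at stable disease. Under the SAP text a PR could be counted.

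**3. Size for ORR.** With the denominator fixed, a cut-off can only remove responses, so omitting it can only raise ORR. One patient moves it by 1/n:
- n = 3: 1/3 = 33.3 points
- n = 6: 1/6 = 16.7 points; the Wilson 95% interval goes from 0–39.0% (0/6) to 3.0–56.4% (1/6)
- n = 75 (planned escalation enrollment, used as a rough ceiling for the evaluable set): 1/75 = 1.3 points; the interval goes from 0–4.9% to 0.2–7.2%

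**4. One patient's PFS record.** The SAP formula is (date − first dose date + 1)/30. Assume surgery on study day 120 and progression on day 240.
- Protocol 5.10.2: censored at (120 − 1 + 1)/30 = 4.0 months
- SAP: event at (240 − 1 + 1)/30 = 8.0 months

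One is a censored time and the other an event time, so the pair shows that the records differ, not that PFS is inflated.

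**5. Direction for Kaplan-Meier estimates.** Assume five PFS events at months 2, 4, 5, 6 and 12, with S(t) the product of (1 − events/at risk).
- SAP as written: S(2) = 4/5 = 0.80; S(4) = 0.80 × 3/4 = 0.60; S(5) = 0.60 × 2/3 = 0.40. Median 5.
- Month-5 patient censored at surgery in month 3: S(2) = 0.80; S(4) = 0.80 × 2/3 = 0.53; S(6) = 0.53 × 1/2 = 0.27. Median 6.
- Month-6 and month-12 patients censored at month 3 instead: S(2) = 0.80; S(4) = 0.80 × 1/2 = 0.40. Median 4.

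The cut-off moves the median up in one case and down in the other.

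**The case against.** The case for treating this as minor has several parts.

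*Scope.* This SAP governs Phase 1 only. A reader might infer that the primary ORR of the expansion cohorts is affected; the documents do not show that, because the Phase 2a plan is separate and was not supplied. This stands.

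*Version.* The SAP follows Amendment 6. The supplied protocol is later, and the relevant paragraph of 5.10.2 mentions palbociclib, whose cohort came with Amendment 7. Whether the censoring sentence existed when the SAP was written cannot be determined. The SAP is also compatible with protocol 7.6, so part of the inconsistency lies within the protocol. This stands as an explanation, but the current documents still disagree.

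*Scoring.* Response is investigator-assessed, and the time-point table in Appendix K 3.4 gives not evaluable when target lesions are not all evaluated. A resected target could arguably be scored that way. So the documents do not support saying that surgical shrinkage would be counted, only that nothing in the SAP prevents it.

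*Bias in durations and disease control.* It is tempting to infer that PFS, DOR and DCB are all inflated. Step 5 shows that this does not follow once an event can be replaced by a censoring. It is equally tempting to add DCR to the inflated measures, but a patient allowed to continue because of clinical benefit would usually already have stable disease or better, so DCR would rarely change.

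*Informative censoring.* Needing local therapy may itself signal a worsening course, so the protocol's rule is not free of bias either. This stands and argues for a sensitivity analysis, not for leaving the rule out.

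**Conclusion.** The discrepancy is confirmed. Protocol 5.10.2 requires efficacy to be cut off at permitted concurrent surgery or radiation. The Phase 1 SAP has no such rule for any of its activity endpoints and does not declare the departure.

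Its effect on ORR can only be upward: 17 to 33 points per affected patient in a cohort of 6 to 3, and about 1.3 points if all 75 planned escalation patients were evaluable. This assumes that the treated lesion was a target lesion, that it was large enough to carry the sum past 30%, that it was scored as gone or shrunken, and that the patient had not already responded. The number of such patients is not given and may be zero. For PFS, DOR and DCB the direction is undetermined.

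This is a reconciliation worth making before the Phase 1 analysis is run. It does not touch the toxicity-based primary objectives.

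**What to change.** In SAP 4.2:
- Censor PFS, DOR and DCB at the last adequate tumor assessment before permitted concurrent anticancer surgery or radiation.
- Use only assessments before that date for BOR, ORR, DCR and TTR, and keep the patient in the denominator. This gives the protocol's word for censoring a meaning for proportions, which it now lacks.
- List each affected patient with the procedure and its date.
- Add a sensitivity analysis that ignores the procedure, because the censoring may be informative.

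Add a cross-reference in protocol 7.6, and make sure that the separate Phase 2a plan has the same rule. Extending the cut-off to later lines of therapy would be a further choice; 5.10.2 does not require it.

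The cost is a few sentences, one listing and one extra analysis. The documents do not say outright that dates of on-study procedures are recorded: the concomitant-therapy sections describe medications, and collection of later therapies in follow-up is for expansion patients only. However, each case needs Medical Monitor permission, so the sponsor will know of it and can obtain the date. The downside is slightly less follow-up for a few patients, and possibly informative censoring, which the sensitivity analysis addresses.

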- Levels of biomarkers (e.g., p53, MDM2, and MDMX gene sequence and copy number, as well as p21 RNA and/or protein expression) in tumor biopsy samples, and in blood, CTCs, where detectable, or MNC samples
- Incidence of anti-ALRN-6924 antibodies

Study Endpoints – Phase 2a dose expansion in MDM2 amplified or MDM2/CDK4 co-amplified solid tumors (ALRN-6924 plus palbociclib)

Primary endpoints:

- The proportion of efficacy-evaluable patients who achieve complete response (CR) or partial response (PR), per investigator assessment, in accordance with RECIST 1.1 or iRECIST (for solid tumor patients) or Response Assessment in Neuro-Oncology (RANO) criteria (for glioblastoma patients).
- Safety and tolerability including the occurrence of adverse events (AEs) and serious adverse events (SAEs), and changes from baseline in vital signs, laboratory analytes, and physical examination findings

Secondary endpoints:

- PK parameters, including AUC, C_{max} , T_{max} , and $t_{1/2}$ for ALRN-6924, its metabolites, and palbociclib
- The median time, in months, from the first response of CR or PR to disease progression or death from any cause (DOR)
- The median time, in months, for each of the following:
 - The first dose of ALRN-6924 to the first response of CR or PR (TTR)
 - The first dose of ALRN-6924 to disease progression or death from any cause (measured at 1 year and beyond) (PFS)
 - The first dose of ALRN-6924 to death from any cause (measured at 1 year and beyond) (OS)

Exploratory endpoint:

- The correlation of response with MDM2, MDMX, and/or CDK4 gene copy number and other genetic and protein biomarkers

Study Design

This is a Phase 1/2a open-label, multi-center, dose-escalation and dose expansion study designed to evaluate the safety, tolerability, PK, PD, and anti-tumor effects of ALRN-6924 administered by IV infusion using up to 4 different dosing regimens of a 28- or 21-day cycle (alone or in combination), in patients with advanced solid tumors or lymphomas with WT TP53 (see p53 Status Determination below). In Phase 1 and Phase 2a, patients will receive ALRN-6924 either once weekly for three consecutive weeks for a 28-day cycle (1 and 2 hour infusions may be tested) or twice weekly for two consecutive weeks for a 21-day cycle. In Phase 2a, dosing three times a week for one week over a 21-day cycle will be tested.

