2.2.2 Secondary Objectives

- Describe the PK of ARLN-6924 and its metabolites in blood following single and multiple IV infusions in patient populations selected for dose expansion with single agent therapy
- Assess duration of response (DOR)
- Assess progression-free survival (PFS)
- Assess overall survival (OS)

- Assess PFS and OS at 1 year
- Assess time to response (TTR)
- Assess the effect of ALRN-6924 treatment on potential pharmacodynamic (PD) biomarkers in tumor biopsy samples (including bone marrow aspirates, where clinically indicated) by measuring potential biomarkers such as p53, p21, caspase, MDM2, MDMX and in blood samples by measuring potential biomarkers such as macrophage inhibitory cytokine-1 [MIC-1] and assessing possible correlation between these biomarkers and clinical outcomes
- Investigate the immunogenicity of ALRN-6924

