2.3.2 Secondary Objectives

- Describe the PK of ALRN-6924 (and its metabolites) and palbociclib when administered in combination
- Estimate DOR
- Estimate additional measures of efficacy, including TTR, PFS, OS, and PFS and OS at 1 year

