6.13 End of Treatment and End of Study

Approximately 30 days (+/- 5 days) after the last dose of study drug, an end of treatment visit will be conducted. For patients in Phase 1, this visit will be the same as the end of study. Patients in Phase 2 will remain on study and be followed for survival and subsequent therapies.

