8.1 Adverse Event Definitions

8.1.1 Adverse Event

An AE includes any noxious, pathological, or unintended change in anatomical, physiological, or metabolic functions as indicated by physical signs, symptoms, and/or laboratory changes occurring in any phase of the clinical study whether or not temporally associated with the administration of study medication and whether or not considered related to the study medication. This definition includes an exacerbation of pre-existing medical conditions or events, intercurrent illnesses, hypersensitivity reactions, drug interactions, or clinically significant laboratory findings.

An AE does not include the following:

- Medical or surgical procedures, e.g., tooth extraction, transfusion, surgery (The medical condition that leads to the procedure is to be recorded as an AE.)
- Pre-existing conditions or procedures present or detected at the start of the study that do not worsen
- Hospitalization for elective surgeries or for other situations in which an untoward medical event has not occurred
- Abnormal laboratory value, unless it is clinically significant according to the Investigator, requires intervention, or results in a delay, discontinuation or change in the dose of study drug
- Overdose of study drug or concomitant medication unaccompanied by signs/symptoms; if sign/symptoms occur, the final diagnosis should be recorded as an AE.
- Pregnancy by itself, unless a complication occurs during pregnancy leading to hospitalization; in this case, the medical condition that leads to the hospitalization is to be recorded as the AE.
- A significant worsening of the disease under investigation including death which is captured as an efficacy parameter in this study and, thus, is not recorded as an AE.

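### Read literally, Protocol 5.10.2 censors overall survival at permitted surgery or radiation, which conflicts with the OS definition and with section 7.6

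*Protocol*

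**What the plan says.** **The censoring rule.** Protocol section 5.10.2 covers a patient who is benefiting from study treatment but "requires concurrent anticancer surgery or radiation therapy, that patient may continue on the study with permission of the Medical Monitor". It then states: "Efficacy measures will be censored, as of the time of any such permitted concurrent therapy". No endpoint is named or exempted, and the section is not limited to one phase or cohort.

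**How OS is classed.** For the palbociclib combination cohort, section 2.3.2 sets the objective "Estimate additional measures of efficacy, including TTR, PFS, OS, and PFS and OS at 1 year", and the synopsis says the same. For PTCL, section 2.2.2 lists OS as a secondary objective without calling it a measure of efficacy. Section 8.1.1, on what not to record as an adverse event, refers to "A significant worsening of the disease under investigation including death which is captured as an efficacy parameter in this study".

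**How OS is defined and followed.** The synopsis endpoint for the combination cohort is "The first dose of ALRN-6924 to death from any cause (measured at 1 year and beyond) (OS". Section 6.13 adds: "Patients in Phase 2 will remain on study and be followed for survival and subsequent therapies". The long-term follow-up footnotes in Appendices D, F, H and J set contact about every 2 months.

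**How OS is to be analysed.** Section 7.6 says: "Additional clinical activity analyses in the Phase 2a dose expansion will include OS and PFS and OS at 1 year". It then runs time-to-event endpoints from first dose to the event or the end of the study. It neither mentions the 5.10.2 rule nor exempts OS from it.

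**The SAP.** Section 3.1 limits the SAP to Phase 1 and leaves Phase 2a to a separate plan. Section 4.2 defines no OS endpoint.

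**The concern.** Censoring at local therapy can be argued for measures that depend on tumor assessment, because surgery or radiation changes the lesions being measured. That argument does not carry over to OS. Death remains observable after local therapy, and the protocol keeps collecting it.

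If OS is censored on the date of radiation or surgery, a later death of that patient is known but not counted. Kaplan-Meier estimation then assumes that the censored patient has the same later risk as those still under observation. Here that is doubtful in both directions. To qualify, a patient must be benefiting from treatment, which suggests lower risk. The same patient must also need local anticancer therapy, which suggests higher risk.

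At stake are OS and OS at 1 year, both secondary objectives in Phase 2a. Two programmers could each follow the protocol, one working from 5.10.2 and the other from the OS definition and section 7.6, and produce different curves. In an open-label study, that choice should not be left until outcomes are known.

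**Working it through.** **Step 1: the passages side by side.**

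| Place | Effect on OS after permitted local therapy |
|---|---|
| Protocol 5.10.2 with 2.3.2 | Censored at the therapy date |
| Protocol synopsis, OS endpoint | Continues to death from any cause |
| Protocol 7.6 | Continues to the event or end of study |
| Protocol 6.13 | Survival data still collected |
| SAP 3.1 and 4.2 | Silent: Phase 1 only, no OS endpoint |

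No passage says which rule takes precedence.

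**Step 2: illustration of size.** The documents give no OS figure to reproduce and no expected rate of permitted local therapy. All inputs below are assumptions except the cohort size: 20 is within the 15 to 25 of Protocol 3.3.

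- OS is exponential with median 10 months, so λ = ln 2 / 10 = 0.0693 per month.
- A share f of the patients alive at month 4 receives the therapy then.
- The death hazard afterwards is HR times λ.

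All deaths counted: S(12) = e^(−4λ) × [(1 − f) × e^(−8λ) + f × e^(−8λ·HR)].

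OS censored at therapy: S(12) = e^(−4λ) × e^(−8λ) = 0.758 × 0.574 = 43.5%, whatever f and HR are.

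Deaths lost by month 12, per 20 patients: 20 × e^(−4λ) × f × (1 − e^(−8λ·HR)).

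| f | HR | 1-year OS, all deaths | Error if censored (points) | Deaths lost / all deaths, per 20 |
|---|---|---|---|---|
| 10% | 0.5 | 44.9% | −1.4 | 0.37 / 11.02 |
| 10% | 1 | 43.5% | 0 | 0.65 / 11.29 |
| 10% | 2 | 41.7% | +1.9 | 1.02 / 11.67 |
| 20% | 0.5 | 46.3% | −2.8 | 0.73 / 10.74 |
| 20% | 1 | 43.5% | 0 | 1.29 / 11.29 |
| 20% | 2 | 39.8% | +3.7 | 2.03 / 12.04 |
| 30% | 0.5 | 47.7% | −4.2 | 1.10 / 10.46 |
| 30% | 1 | 43.5% | 0 | 1.94 / 11.29 |
| 30% | 2 | 38.0% | +5.6 | 3.05 / 12.41 |

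Errors are computed before rounding. For f = 10% and HR = 2, for example, 43.53 − 41.67 = 1.86.

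**Step 3: sensitivity to timing and median.** A simulation used medians of 9 and 12 months and therapy spread evenly over months 2 to 8. With HR from 0.5 to 2, the error was about −1.3 to +1.7 points with 10% of patients selected, −2.6 to +3.3 with 20%, and −3.7 to +5.1 with 30%. The share of first-year deaths discarded was about 3 to 8%, 6 to 16% and 9 to 23% respectively. At HR = 1 the error was zero within simulation noise, although deaths were still lost.

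**Step 4: comparison with sampling error.** At n = 20 and 1-year OS of 43.5%, ignoring censoring, the standard error is √(0.435 × 0.565 / 20) = 0.111, or about 11 points.

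**The case against.** The strongest reply is that this is loose drafting and not a settled analysis rule. The censoring sentence sits in a concomitant-medication section and never mentions survival or death. The passages that define and analyse OS run it to death or the end of the study, and a sensible statistician would let them govern. Full statistical detail for Phase 2a is deferred to a plan that is not among the documents. This has force. A reader might infer that deaths after local therapy will certainly drop out of Phase 2a OS, but the documents do not support that, because they contain both rules and rank neither.

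Three further limits stand:

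- **Scope of the label.** OS is expressly called a measure of efficacy only for the palbociclib cohort. For PTCL, which may supply up to three of the five expansion cohorts, the reading rests on the study-wide reach of 5.10.2. Section 8.1.1 adds only weak support, since it is an adverse-event recording rule and does not define OS.
- **Later systemic therapy.** A reader might infer that systemic therapy after the study leaves OS uncensored while radiation does not. Section 6.13 only says that subsequent therapies are recorded. It is not a censoring rule, so the contrast would be drawn from silence.
- **Size.** The exception needs clinical benefit, a need for local therapy, and the Medical Monitor's permission. Nothing in the documents suggests that it will reach 20 or 30% of patients.

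The reply does not remove the problem. The 5.10.2 wording has no exemption, section 2.3.2 uses almost the same term for OS, and no document supplied says that OS is outside the rule.

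**Conclusion.** The concern holds as a conflict to be resolved before Phase 2a is analysed. The literal 5.10.2 rule gives the wrong treatment of OS, and the definition and section 7.6 give a different one.

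The direction of any bias is unknown. A reader might expect the rule to flatter survival, but the table shows that it can equally understate it. The size depends entirely on assumed inputs. It is zero if later risk is unchanged, about 1 to 2 points of 1-year OS if 10% of patients are affected, and up to about 5 points if 30% are, with the later death hazard halved or doubled. Each of these is below the sampling standard error of about 11 points at n = 20.

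OS is secondary, the analyses are descriptive (Protocol 7.1), and the deaths are still collected, so nothing is lost for good. The change is still worth making because the rule as worded is wrong for OS and the remedy is small.

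**What to change.** Three statements are needed:

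1. **PFS, DOR and TTR:** limit the 5.10.2 censoring to these time-to-event measures.
2. **ORR:** count only responses documented before the concurrent therapy, and keep the patient in the denominator. ORR is a proportion and cannot be censored, so the present sentence leaves this primary endpoint without a usable rule.
3. **OS:** not censored for concurrent or subsequent therapy. It runs to death from any cause and is censored only at the date last known alive or at data cut-off.

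The OS statement can go in 5.10.2 or in the Phase 2a SAP. Changing 5.10.2 is a protocol amendment and needs IRB approval under Protocol 9.4. If no amendment is otherwise due, the pending Phase 2a SAP can carry the statements and record them as a clarification of 5.10.2. No new data are needed, because survival follow-up is already planned. The date of any permitted surgery or radiation must be available to the analysis, as the present rule already requires.
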